8.1.11. Destruction and Return

Any unused product or waste material should be disposed of in accordance with local requirements.

9. BIOMARKER, CORRELATIVE, AND SPECIAL STUDIES

9.1. Laboratory Correlative Studies

Throughout the study, at designated time points, patient blood and marrow samples will be collected for correlative analysis. Specifically, we will viably cryopreserve peripheral blood and bone marrow samples serially at baseline, during treatment, and at the end of treatment/time of progression. We will collect blood samples just prior to each infusion of MBG453 during cycles 1-3, and a bone marrow assessment will be performed at baseline, after cycle 2, after cycle 4, and then per the treating investigator. Peripheral blood and bone marrow samples will be collected at end of treatment or progression.

9.1.1. Correlative Study 1: Characterize the impact of TIM-3 Inhibition on MDS progenitor and T-cell subsets

Background: We propose an exploratory correlative study to characterize the effect of TIM3 inhibition on the MDS progenitor cells as well as T-cell subsets. We have previously developed a mass cytometry panel that assesses peripheral blood T-cells, myeloid components, and bone marrow cells with specific attention to markers relevant to MDS and immune checkpoint targets. The primary aim of this correlative will be to use mass cytometry to better characterize intra-patient changes in T-cell and myeloid cell

populations during treatment with MBG453. This work will be done in coordination with the laboratory of [name] (MGH Vaccine and Immunotherapy Center).

9.1.1.1. Collection of Specimen(s)

- Bone marrow biopsies will be performed at baseline (screening), after cycle 2 of treatment, and at EOT. Approximately 10cc of bone marrow aspirate should be collected locally in an EDTA-containing tube(s).
- Peripheral blood will be collected at baseline and just prior to each infusion of MBG453 day 1 of cycles 2, 3, and 5, on day 15 of cycles 1-4, and at EOT. Peripheral blood should be collected in 2 10ml EDTA-containing tubes

9.1.1.2. Handling and Shipping of Specimens(s)

Samples will be packaged and shipped per instructions in the laboratory manual. Samples should be shipped Monday through Thursday to ensure Friday receipt.

9.1.1.3. Site(s) Performing Correlative Study

This work will be done in the laboratory of [name] (MGH Vaccine and Immunotherapy Center).

9.1.2. Correlative Study 2: Exploring genetic factors associated with response and progression

Background: We will perform serial NGS-based testing for recurrent myeloid somatic mutations to characterize subclonal MDS changes during treatment. We will use these data to explore the biological response to MBG453 including mutations that confer sensitivity to treatment, and emerging mutations as putative escape mechanisms. We will collect standard tumor characteristics including tumor subtype, cytogenetics, cell surface markers, molecular abnormalities, both at study entry and during treatment. We will analyze whether certain MDS characteristics are associated with a specific response to therapy or change in cell populations. NGS-based testing will be performed per local institutional standards at with bone marrow biopsies at Baseline, C3D1, and End of Treatment (EOT). In the event of a dry tap, peripheral blood may be substituted.

10. STUDY CALENDAR

All screening evaluations must be conducted within 21 days of the start of protocol therapy. If the participant's condition is deteriorating, laboratory evaluations should be repeated within 48 hours prior to initiation of the next cycle of therapy. Assessments must be performed prior to administration of any study agent. Study assessments and agents should be administered within \pm 3 days of the protocol-specified date, unless otherwise noted.

Standard safety assessments will be conducted at screening, during the study treatment and as scheduled during the safety follow up period. A visit should be planned at EOT and end of the safety follow up period (150 days after last dose of MBG453).

Local clinical laboratories can be used for the analysis of scheduled hematology, chemistry and other

blood specimens collected as part of safety monitoring. It is preferable to use the same laboratory for all the assessments performed.

- **Troponin-T** should be included among the regular blood chemistry parameters to monitor for cardiac toxicity.
- To monitor **thyroid** toxicity, TSH, Free-T3 and Free-T4 should be measured at screening. TSH should be monitored regularly (at selected visits) during treatment and as clinically indicated. If TSH is abnormal, then test free-T3 and free-T4.
- MDRD equation should be used to calculate eGFR at screening.
- Amylase and lipase should be monitored with serum chemistries

Local ECGs should be planned among regular safety assessment (vitals and physical examination) pre-dose on D1 of each cycle and at EOT, and may be stored as source documents.

	Screening	Cycles 1 - 2				Cycles 3 - 4		Cycle 5 onwards	End of Treatment ^d	Safety / Survival	EDC Timepoints
		Day 1 ^b	Day 8 ± 3 days	Day 15 ± 3 days	Day 22 ± 3 days	Day 1	Day 15 ± 3 days	Day 1	30 days after last dose	30, 150, 250 days, 1 year	
MBG453		X				X		X			Day 1 of every cycle
Informed consent	X										N/A
Demographics	X										Screening
Medical history	X										Screening
Concurrent meds, including transfusion history	X	X----- X									N/A
Physical exam	X	X				X		X	X		Screening
Vital signs	X ^e	X	X	X	X	X	X	X	X		Screening
Height	X										Screening
Weight	X	X				X		X	X		Screening
Performance status (ECOG)	X	X				X		X			Screening
CBC w/diff, plts	X	X	X	X	X	X	X	X	X		Screening, C1-2 day 1, 8, 15, 22, C3-4 day 1, 15, the day 1 of every cycle, and EOT/each follow up
Serum chemistry ^a	X	X	X	X	X	X	X	X	X		Screening, C1-2 day 1, 8, 15, 22, C3-4 day 1, 15, the day 1 of every cycle, and EOT/each follow up
Troponin-T	X	X	X	X	X	X		X	X		Screening, C1-2 day 1, 8, 15, 22, C3-4 day 1, 15, the day 1 of every cycle, and EOT/each follow up
TSH, free T3, free T4 ⁱ	X	X ^j				X ^j		X ^j	X ^j		Screening, day 1 of every cycle, EOT
PT/INR, PTT, fibrinogen, ddimer	X										Screening
ECG	X	X				X		X	X		Screening, day 1 of every cycle, EOT
Adverse event evaluation		X----- X								X ⁱ	During all visits
Transfusions administered	Assess prior 16 week transfusions	X----- X									
B-HCG	X ^b	X				X		X	X	X	Screening, day 1 of every cycle, EOT, safety
Serum EPO level	X										Screening
Bone Marrow Biopsy ^c	X					C3D1		C5D1 ^e	X		Screening, cycle 3 day 1, cycle 5 day 1, EOT, and any additional marrow

											assessments while on treatment
NGS (Rapid Heme Panel) ^k	X					X				X	With bone marrow biopsies at screening, cycle 3 day 1, and EOT/progression
Peripheral Blood for correlatives	X	C2D1 only		X		C3D1	X	C5D1 ^c	X		
Bone marrow aspirate for correlatives ^f	X					C3D1		C5D1 ^c	X		
Follow up										X ⁱ	Safety/Survival

a: Albumin, alkaline phosphatase, total bilirubin, direct bilirubin, bicarbonate or CO₂, BUN, calcium, chloride, creatinine, glucose, LDH, phosphorus, potassium, magnesium, total protein, SGOT [AST], SGPT [ALT], sodium, uric acid, amylase, lipase.
 
b: Serum pregnancy test (women of childbearing potential, WOCP). At screening, a serum pregnancy test (serum β-HCG) must be performed within 3 days before the first dose for WOCP. During the study, a urine / serum pregnancy test should be done at Day 1 of each cycle for WOCP (except Cycle 1 if a pregnancy test had been performed within 72 hours of the first dose) and at EOT visit. A pregnancy test (serum or urine) should be performed every month during the safety follow-up period for WOCP (until day 150). If the patient is not coming to the clinic during the safety follow-up, it can be performed at home or at a local doctor's office, and the results will be communicated to the site staff.
 
c: Bone marrow biopsy and aspirate should be performed at baseline, cycle 3 day 1 ±3 days, and then within 7 days of cycle 5 day 1, at end of treatment, and as clinically indicated. Standard institutional testing including cytogenetics and molecular testing is recommended.
 
d: Off-treatment evaluation. The in-person visit has a window of ±3 days; additional safety follow-up is required through day 150. Note: for IND/IDE trials, follow up visits or other contact are required in order to identify SAEs during the 30 days following the end of study treatment. After end of treatment visit, patients should be followed per section 5.7 for survival and progression.
 
e: Bone marrow assessment for cycle 7 and cycle 11 may be done up to 7 days prior to the start of the treatment cycle. If a patient has a bone marrow assessment within 1 cycle of the planned assessment (e.g. cycle 6 or cycle 10) this may be used for the study assessment. A bone marrow for research samples will be performed on cycle 1 day 3 (window day 3-6).
 
f: Bone marrow samples for correlative studies will be collected at baseline, at cycle 3 day 1, and EOT for both NGS testing and for cytof analysis.
 
g: Blood pressure, heart rate, and temperature will be performed at screening and then as clinically indicated. . Bone marrow biopsy on cycle 5 day 1 will only require Cytof samples to be obtained.
 
h: On C1D1, total bilirubin, direct bilirubin, creatinine, SGOT [AST], SGPT [ALT], and INR should continue to meet inclusion criteria. Baseline values will be those assessed on C1D1
 
i: Follow up to evaluate for progression and survival may be ±7 days from those noted (day 30, 150, 250, and 1 year). Safety evaluations must be through 150 days after the last dose of MBG453. The safety follow up can be done by telephone call or visit. The information collected is kept as source documentation. All SAEs reported during this time period must be reported as described in Section 7.3. Documentation of attempts to contact the subject should be recorded in the source documentation.
 
j: TSH, free T3, and free T4 should be obtained during screening. TSH should be monitored regularly (at selected visits) during treatment and as clinically indicated. If TSH is abnormal, then test free-T3 and free-T4.
 
k: Rapid Heme Panel for NGS should be collected as part of standard of care with bone marrow biopsies at screening, C3D1 (+/-3 days), and EOT/progression. In the event of a dry tap, peripheral blood may be substituted.
											

11. MEASUREMENT OF EFFECT

Response to therapy will be assessed based on the proposal for the modification of the International Working Group (IWG) response criteria in myelodysplasia (Cheson et al., 2006), but modified to include complete remission with partial hematologic improvement CRh (Bloomfield et al., 2018), and the 2018 proposed update for hematologic responses and transfusion independence (TI) (Platzbecker et al., 2019). Patients with dysplastic-type CMML will use MDS risk-stratification and response assessment criteria.

11.1. Antitumor Effect – MDS

Complete remission (CR): patients must have a bone marrow with ≤ 5% myeloblasts and with normal maturation of all cell lines. Persistent dysplasia may be noted. Blood counts over a duration of at least 4 weeks should show a hemoglobin ≥ 11 g/dL, platelets ≥ 100,000/uL, and absolute neutrophil count ≥ 1000/uL, without circulating blasts in the peripheral blood.

Partial remission (PR): over a duration of at least 4 weeks, all CR criteria (if abnormal prior to treatment) except:

1. Bone marrow blasts have decreased $\geq 50\%$ over pre-treatment levels but are still $> 5\%$, if elevated at baseline
2. Cellularity and morphology are not considered relevant

Marrow Complete Remission (mCR): over a duration of at least 4 weeks, bone marrow showing $\leq 5\%$ myeloblasts and with a decreased of $\geq 50\%$ over pre-treatment levels. If the peripheral blood counts show evidence of hematologic improvement responses, these will be noted in addition to the marrow CR.

Complete Remission with Partial Hematologic Recovery: $< 5\%$ blasts in the bone marrow and partial recovery of peripheral blood counts (platelets $> 50 \times 10^9/L$ and ANC $> 0.5 \times 10^9/L$).

Stable disease (SD): failure to achieve at least PR, but without evidence of progression for > 8 weeks.

Hematologic Responses According to the 2006 Hematologic Response Criteria:

Hematologic Improvement: HI is assessed in addition to CR/PR/mCR/SD.

1. Erythroid response: pretreatment level < 11 g/dL, showing a hemoglobin increase by ≥ 1.5 g/dL over at least 8 weeks
2. Platelet response: pretreatment level $< 100,000/uL$; showing:
 - a. Absolute increase $\geq 30,000$ if baseline $> 20,000$
 - b. Absolute increase $> 20,000$ and by at least 100% increase if baseline $< 20,000$
3. Neutrophil response: pretreatment level $< 1000/uL$, showing an absolute increase $> 500/uL$ and at least a 100% increase

Transfusion Independence: pretreatment requirement of at least 4U RBC within an 8 week period for a Hgb < 9 g/dL, no transfusions needed over an 8 week period

Hematologic Responses According to Proposed 2018 Hematologic Response Criteria:

We will also collect responses according to the proposed 2018 criteria. Patients will be categorized at baseline based on transfusion needs in the prior 16 weeks into three groups:

1. Non-transfusion Dependent (NTD): 0-2 RBCs in 16 weeks
2. Low Transfusion Burden (LTB): 3-7 RBCs in at least 2 transfusion episodes, maximum of 3 in a given 8 week period
3. High Transfusion Burden (HTB): ≥ 8 RBCs in 16 weeks, ≥ 4 in 8 weeks

IWG 2018 hematologic responses will include:

1. Erythroid Response: pretreatment Hgb level < 10 d/dL
 - a. NTD: At least 2 consecutive Hgb measurements ≥ 1.5 g/dL for a period of minimum 8 weeks in an observation period of 16 to 24 weeks compared with the lowest mean of 2 Hgb measurements (apart from any transfusion) within 16 weeks before treatment onset

- b. LTB: HI-E in LTB patients corresponds to transfusion independence, defined by the absence of any transfusions for at least 8 weeks in an observation period of 16-24 weeks, compared with 16 weeks prior to treatment
- c. HTB:
 - i. Major response: Major HI-E response in HTB patients corresponds to transfusion independence, defined by the absence of any transfusions over a period of minimum 8 weeks in an observation period of 16-24 weeks compared with 16 weeks prior to treatment
 - ii. Minor response: Minor HI-E response in HTB patients is defined as a reduction by at least 50% of RBCs over 16 weeks
2. Platelet response: pretreatment level < 100,000/uL; showing:
 - a. Absolute increase \geq 30,000 if baseline > 20,000
 - b. Absolute increase > 20,000 and by at least 100% increase if baseline < 20,000Increments of platelets will be reported for patients with pretreatment platelets >100k
3. Neutrophil response: pretreatment level < 1000/uL, showing an absolute increase > 500/uL and at least a 100% increase. Increments of neutrophils will be reported for patients with a pretreatment ANC > 1000.

Overall Response Rate

The overall response rate (ORR) will be defined as CR + PR + CRh + HI + TI. It will be reported using both the 2006 and 2018 criteria above but the primary endpoint will be based on the 2006 criteria.

Patients not meeting one of the above criteria are considered to have a failed response (see “Failure,” below).

The following response measures may be assessed in addition to/subsequent to the above.

Cytogenetic response:

1. Complete response is the disappearance of the chromosomal abnormality without the appearance of new ones
2. Partial response is at least 50% reduction of the chromosomal abnormality

Progression of disease:

1. For patients with <5% blasts: \geq 50% increase in blasts to > 5% blasts
2. 5-10% blasts: \geq 50% increase in blasts to > 10% blasts
3. 10-20% blasts: \geq 50% increase in blasts to > 20% blasts
4. Progression/relapse from HI:
 - a. Reduction in hemoglobin by \geq 1.5 g/dL
 - b. \geq 50% decrease from maximum response in granulocytes or platelets
 - c. Transfusion dependence

Relapse after CR or PR: at least 1 of the following:

1. Return to pre-treatment bone marrow blast percentage
2. \geq 50% decrease from maximum response in granulocytes or platelets

3. Reduction in hemoglobin by ≥ 2 g/dL or transfusion dependence

Failure:

Death during treatment, or disease progression characterized by worsening of cytopenias, increased bone marrow blasts, or progression to a more advanced MDS subtype than pretreatment.

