New approaches to transfusion dependence and symptomatic cytopenias in lower-risk MDS are desperately needed. Historically, rates of blood count improvement are low without treatment; in the recent MEDALIST trial (Fenaux et al., 2020), which compared therapy with luspatercept to supportive care alone (placebo), 13% of patients receiving placebo achieved the primary endpoint, and this serves as a historical comparator in identifying new active compounds.

Currently, the only curative therapy for MDS is allogeneic transplant; the mechanism by which allogeneic transplant is effective in MDS is thought to be immune mediated through graft vs. leukemia effect, particularly when using a reduced intensity conditioning regimen (Weisdorf et al., 2012). Even in the absence of allogeneic transplantation, immune checkpoint dysregulation may contribute to disease progression for patients with MDS, CMML, and AML (Aggarwal et al., 2011). T-cell immunoglobulin and mucin domain containing molecule-3 (TIM-3) which is expressed on T-cells as well as on leukemic stem cells in MDS (Asayama et al., 2015; Kikushige et al., 2014, 2010; Tao et al., 2014). Interestingly, while TIM-3 is aberrantly expressed on leukemic blasts, it does not appear to be present on normal hematopoietic stem cells. TIM-3 is expressed on T-cells and plays a role in immune checkpoint control; upon encountering galectin-9 on tumor cells, TIM-3 is phosphorylated and downregulates the T-cell response against the tumor.

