3.1 Eligibility Criteria

3.1.1 Lower risk MDS patients (IPSS-R score ≤ 3.5 at diagnosis) who have progressed or are refractory to/intolerant of prior therapy and meet one of the following categories:

- RBC transfusion dependent according to IWG criteria must either be unresponsive to prior ESA therapy or have an EPO level > 500
- Prior HMA therapy
- Patients with the following cytopenias who otherwise are felt to require treatment per the treating physician:
 - Platelets $< 50k/uL$
 - ANC < 500 cells/uL
- Patients with MDS with isolated del(5q) (“5q- syndrome”) must have progressed on or not tolerated lenalidomide
- Patients who are not felt to be candidates for or lack other standard treatment options. Patients with prior luspatercept exposure are eligible.
- Patients with dysplastic type CMML (WBC $< 13,000$ cells/uL) meeting the above criteria are eligible; responses will be assessed using MDS criteria

3.1.2 Age ≥ 18 years. Because no dosing or adverse event data are currently available on the use of MGB453 in participants < 18 years of age, children are excluded from this study, but will be eligible for future pediatric trials.

3.1.3 ECOG performance status ≤ 2 (see Appendix A).

3.1.4 Participants must have adequate organ and marrow function as defined below within 21 days of treatment:

- Total bilirubin ≤ 2 mg/dL (unless due to Gilbert’s in which case it must be < 3 mg/dL)
- AST(SGOT)/ALT(SGPT) $\leq 3 \times$ institutional ULN
- Creatinine clearance ≥ 30 mL/min/1.73 m² (by MDRD calculation)

3.1.5 Human immunodeficiency virus (HIV)-infected participants on effective anti-retroviral therapy with undetectable viral load over the prior 6 months are eligible for this trial.

3.1.6 Participants with known history or current symptoms of cardiac disease, or history of treatment with cardiotoxic agents, should have a clinical risk assessment of cardiac function using the New York Heart Association Functional Classification. To be eligible

for this trial, participants should be class 2B or better.

3.1.7 Ability to understand and the willingness to sign a written informed consent document.

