13.1. Study Design/Endpoints

The primary objective is to evaluate the ORR of MBG453 in lower-risk MDS after standard front-line therapy. The ORR will be comprised of CR, PR, HI, TI, and CRh, as described in section 11.1. We will assess response as the best overall response within the first 6 months of treatment.

Secondary endpoints include:

- The rates and severity of adverse events associated with MBG453 in lower risk MDS
- The rates of 1-year overall survival (OS), progression free survival (PFS), time to disease progression, and duration of response to therapy with MBG453.
- Response to therapy according to pretreatment disease and patient characteristics, monitoring disease-specific molecular, immunophenotypic, and cytogenetic evolution during treatment (exploratory analysis)
- Changes in cell surface marker expression, Immune cell subsets, and molecular clonal evolution during treatment and at the time of progression (exploratory analysis)

This study will follow a Simon's Optimal Two-Stage Phase II design. The null hypothesis that the true response rate is $P=0.15$ will be tested against a one-sided alternative. In the first stage, 10 patients will be accrued. If there are no more than 1 responses in these 10 patients, the study will be stopped. Otherwise, 12 additional patients will be accrued for a total of 22. The null hypothesis will be rejected if 6 or more responses are observed in 22 patients. This design yields a type I error rate of 0.09 and power of 0.80 when the true response rate is 0.35.

In order to closely monitor for signals of toxicity in the lower-risk MDS cohort, we will assess

the first six patients who are enrolled for dose limiting toxicities (DLTs) during the first 28 days of treatment. If more than 1 of the first 6 patients experiences a DLT the study enrollment will stop and reviewed for safety prior to further enrollment. The following table provides the probability that no more than 1 in 6 patients experiences a DLT and the study proceeds without interruption, given the true but unknown rate of DLT:

	True but unknown probability of experiencing a DLT				
	0.10	0.20	0.30	0.40	0.50
Pr(success)	0.89	0.66	0.42	0.23	0.11

Follow-up will be planned 1 year after end of treatment or death, whichever occurs first. The toxicities will be measured according to NCI-CTC version 5.0 (<http://ctep.info.nih.gov>), and tabulated according to the stage of dose escalation.

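### CRh counts in the primary ORR without any baseline condition, so a patient who already meets it at entry can be scored a responder with no change

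*Combined protocol and SAP*

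**What the plan says.** Section 11 takes the 2006 IWG criteria, "modified to include complete remission with partial hematologic improvement CRh". Section 11.1 then gives the operative definition of CRh: fewer than 5% "blasts in the bone marrow and partial recovery of peripheral blood counts", the recovery being specified in parentheses as platelets above 50 x10^9/L and ANC above 0.5 x10^9/L. Hemoglobin, transfusion need, duration and pretreatment status are not mentioned.

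CRh feeds the primary endpoint. Section 11.1 states: "The overall response rate (ORR) will be defined as CR + PR + CRh + HI + TI". Section 13.1 repeats it: "The ORR will be comprised of CR, PR, HI, TI, and CRh, as described in section 11.1". Response is the best achieved in the first 6 months.

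Most neighbouring definitions in 11.1 do look back to baseline. PR requires "all CR criteria (if abnormal prior to treatment) except" for the marrow elements. Marrow CR needs a blast fall of at least 50% from pretreatment. HI needs a low pretreatment value and a rise. TI needs at least 4 RBC units in 8 weeks before treatment. Stable disease is "failure to achieve at least PR, but without evidence of progression for > 8 weeks".

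Section 3.1 lists alternative entry categories, one of which is enough. One of them reads: "RBC transfusion dependent according to IWG criteria must either be unresponsive to prior ESA therapy or have an EPO level > 500". It carries no upper limit on platelets or ANC, and section 3.1 sets no minimum blast percentage.

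**The concern.** A transfusion-dependent patient with under 5% blasts, platelets above 50 and ANC above 0.5 x10^9/L is eligible and satisfies every CRh number before the first dose. If nothing changes, the on-study marrow and blood count satisfy them again. Taken literally, the patient is a responder while still transfusion dependent. The same patient fits stable disease, and the plan gives no order of precedence, so two assessors could score the same data in opposite ways.

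The null rate of 0.15 is meant to describe what happens without active treatment. Section 2.1 supports it this way: "Historically, rates of blood count improvement are low without treatment", with 13% of placebo patients in the cited trial reaching its primary endpoint. That is a rate of improvement. An endpoint that also credits an unchanged state has a higher background rate, so the type I error and the chance of stopping an inactive drug at stage 1 would no longer be those planned. With 22 patients and a success threshold of 6, a few such credits matter.

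**Working it through.** **Inputs from section 13.1.** Null rate 0.15, alternative 0.35. Stage 1: 10 patients, stop if 1 or fewer respond. Stage 2: 12 more, 22 in all; reject the null if 6 or more respond. Stated type I error 0.09, power 0.80.

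**Input not in the documents.** The number or share of patients who meet CRh at baseline and are credited. It is varied below.

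**Step 1: reproduce the plan's figures.** With response probability p,

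P(reject) = sum over x = 2 to 10 of Bin(x; 10, p) × P(Bin(12, p) ≥ 6 − x)

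P(stop at stage 1) = (1 − p)^10 + 10p(1 − p)^9

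- p = 0.15: P(reject) = 0.0907; P(stop) = 0.1969 + 0.3474 = 0.5443.
- p = 0.35: P(reject) = 0.8040.

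The stated 0.09 and 0.80 are correct. The difficulty is in the endpoint definition, not in the design arithmetic.

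**Step 2: who can meet CRh at entry?**

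- Patients who enter with platelets below 50k or ANC below 500 fail CRh at baseline and cannot be credited for an unchanged state.
- Patients who enter by another route (RBC transfusion dependence, prior HMA, lack of other options) face no such limit.
- Patients with under 5% blasts are expected: the progression criteria in 11.1 have a separate row for them.
- CR has no explicit baseline condition either, but it needs hemoglobin of at least 11 g/dL with higher platelet and ANC levels over at least 4 weeks, so an unchanged transfusion-dependent patient with low hemoglobin would not meet it.

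**Step 3: a fixed number k credited without change.** The k patients fall at random among the 22 (hypergeometric split over the two stages); the other 22 − k respond at 0.15. For k = 1, the credited patient is in stage 1 with probability 10/22, and the trial then stops only if the other 9 all fail (0.85^9 = 0.2316). Hence P(stop) = (10/22)(0.2316) + (12/22)(0.5443) = 0.4022.

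| k credited of 22 | P(declare inactive drug active) | P(stop at stage 1) |
|---|---|---|
| 0 | 0.0907 | 0.5443 |
| 1 | 0.1801 | 0.4022 |
| 2 | 0.3233 | 0.2758 |
| 3 | 0.5170 | 0.1770 |
| 4 | 0.7264 | 0.1065 |

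**Step 4: a share q credited without change.** The null response probability becomes p = q + (1 − q)(0.15).

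| q | p | P(declare active) | P(stop at stage 1) |
|---|---|---|---|
| 0 | 0.150 | 0.0907 | 0.5443 |
| 2.5% | 0.171 | 0.1475 | 0.4687 |
| 5% | 0.193 | 0.2181 | 0.3989 |
| 10% | 0.235 | 0.3872 | 0.2795 |
| 20% | 0.320 | 0.7181 | 0.1206 |

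Here q is the share actually credited. If assessors credited only half of those who qualify, a baseline share of 10% would be read at q = 5% (0.22) and one of 20% at q = 10% (0.39).

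**The case against.** The strongest reply is that the plan's words imply change. Section 11 speaks of improvement, section 11.1 of remission and recovery, and section 2.3 asks that patients entering for other cytopenias have ones that can be assessed for response. A sensible assessor might refuse to credit an unchanged patient, and a null of 0.15 against a target of 0.35 suggests that the authors did not intend such credit. Section 11 also cites a publication for CRh, which may carry a baseline condition that cannot be checked from these documents.

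All of this bears on intent, and the intent was probably as described. But the parenthesis in 11.1 turns recovery into a numerical test, no rule enforces a prior deficit, and nothing settles CRh against stable disease. A single-arm primary endpoint should not rest on an assessor's inference.

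Three further points stand in part. The size is conditional on an undocumented number, and choosing among 1 to 4 patients is illustrative. The stage 1 rule still operates; what changes is how often it stops an inactive drug. And with no credits the error rate is 0.09 only if 0.15 is the true background rate of the whole composite, which is the plan's own assumption.

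**Conclusion.** The concern holds. As written, CRh can be credited to an eligible patient whose disease has not changed, and that credit enters the primary ORR. The planned type I error of 0.09 applies only if no patient is credited this way and the plan's null of 0.15 is right for the remaining components. Under that same null, one credited patient in 22 about doubles the error, to 0.18, and three bring it to 0.52; the chance of stopping an inactive drug at stage 1 falls from 0.54 to 0.40 and 0.18. How many patients would be affected is unknown, and the number could be zero if assessors read a prior deficit into the definition. The gap in the text is certain; its numerical effect is conditional. It should be fixed.

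**What to change.** Add to section 11.1, with a matching line in 13.1:

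> An ORR component is not credited if its criteria were already met at baseline. For CRh, at least one of the blast, platelet and ANC criteria must be unmet at baseline and become met on treatment. A patient who met CRh at baseline and is unchanged is classed as SD, unless CR, PR, HI or TI is met.

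This keeps genuine CRh in the endpoint and settles the overlap with stable disease. It does not supply the missing duration: a single reading just over a threshold would still count. CR and PR beside it require at least 4 weeks, so the authors should also say whether a minimum duration applies to CRh.

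The cost is a few sentences. Baseline marrow and blood counts are already in the study calendar, so no new data are needed. The observed ORR may be lower. Because this clarifies a primary endpoint component in a single-arm trial, the change should be dated, and any response already scored as CRh should be rechecked against baseline; the documents do not give accrual status.
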